4.1.2 CYP450 Drug Interactions (Related to Drug Metabolism)

Strong inhibitors/inducers of CYP3A4 and CYP1A2 and drugs that are known substrates for CYP1A2 and CYP2D6 with a narrow therapeutic index should be used with caution in this study.

Known inhibitors of CYP1A2 include acyclovir and fluvoxamine, and known inhibitors of CYP3A4 include atazanavir, clarithromycin, indinavir, itraconazole, ketoconazole, nefazodone,

nelfinavir, ritonavir, saquinavir, and telithromycin.

Known inducers of CYP1A2 include omeprazole, insulin, and cigarette smoking, and known inducers of CYP3A4 include rifampin and carbamazepine.

Sensitive CYP1A2 substrates with narrow therapeutic indices include theophylline and tizanidine, and sensitive CYP2D6 substrates with narrow therapeutic indices include thioridazine and tamoxifen.

Exceptions are allowed per PI discretion, if clinically indicated.

4.2 MEDICATIONS TO AVOID OR USE WITH PRECAUTION (TMZ)

Administration of valproic acid decreases oral clearance of temozolomide by about 5%.

4.3 G-CSF AND ERYTHROPOIETIN ADMINISTRATION:

Routine prophylactic use is not permitted. However, therapeutic use in patients with complications (severe neutropenia with fever or anemia), may be considered at the investigator's discretion.

4.4 PLATELET SUPPORT:

Prophylactic use of platelet is only used when Platelet count < 20 x 10⁹/L. Platelet transfusion is provided for active bleeding patients with thrombocytopenia to keep platelet count above 50 x 10⁹/L.

4.5 CORTICOSTEROIDS

Should be used in the smallest dose to control symptoms of cerebral edema and mass effect and discontinued if possible.

4.6 FEBRILE NEUTROPENIA

It may be managed according to the local institution's Infectious Disease guidelines. Measures may include appropriate laboratory testing, including blood and urine cultures and the institution of broad-spectrum antibiotics. If a source for the fever is not identified or the fever resolves when the neutrophil count recovers, antibiotics may be discontinued, and the patient observed.

4.7 ANTI-EMETICS

Prophylactic and therapeutic use is allowed. Other concomitant medications and the therapies considered necessary for the well-being of the patient may be given at the discretion of the treating physician. All concomitant medications must be recorded.

4.8 OTHER ANTICANCER OR EXPERIMENTAL THERAPIES

No other anticancer therapy (including chemotherapy, radiation, hormonal treatment or immunotherapy) of any kind is permitted during the study period. No other antitumor drugs under investigation may be used concomitantly with the study drug.

5 BIOSPECIMEN COLLECTION

5.1 CORRELATIVE STUDIES FOR RESEARCH

Test/assay	Volume blood (approx.)	Type of tube	Collection point (+/- 48hrs)	Location of specimen analysis
Target DNA Sequencing	Tumor tissue block	-	Initial and/or Recurrence	Laboratory of Pathology
Western Blot and PCR	Fresh Frozen Tumor	-	Surgery at Disease recurrence	NOB Laboratory
PK and PG*	6mL	Sodium Heparin (green top)	Cycle 1 day -3 at the following time points: pre-dose, 1hr, 2hr (peak), 4hr, 12hr-, 24hr, 48hr, and 72hr post oral dose. For patients in the cohort expansion only	[name]
	Up to 6mL	EDTA (purple top)	Cycle 1 day – 3 For patients in the cohort expansion only	[name]
Neutrophil analysis**	12mL	EDTA (purple top)	Cycle 1 day -3 at the following time points: pre-dose, 1hr, 2hr (peak), 4hr, 12hr, 24hr, 48hr, and 72hr post oral dose. For patients in the cohort expansion only	(1 tube) Processed by NOB Laboratory and sent to Dept of Laboratory Medicine
				(1 tube) Processed by NOB Laboratory and sent to Neutrophil Monitoring Lab (NML)

Test/assay	Volume blood (approx.)	Type of tube	Collection point (+/- 48hrs)	Location of specimen analysis
	6mL	(green top)	Cycle 1 day -3 at the following time points: pre-dose, 1hr, 2hr (peak), 4hr, 12hr, 24hr, 48hr, and 72hr post oral dose. For patients in the cohort expansion only	Processed by NOB Laboratory and sent to Neutrophil Monitoring Lab (NML)

*PK/PG analysis: For patients in Post-Interim Analysis cohort, samples will be collected in Cycle 1 day -3 at the following time points only: pre-dose, 1hr, 2hr (peak), 4hr, 24hr, and 48hr post oral dose.
 
**Neutrophil analysis will not be collected and performed in patients in Post-Interim Analysis cohort.
				

5.1.1 The brain tumor tissue block from initial and /or recurrence will be collected to detect MGMT methylation, *TP53*, *PTEN*, *IDH* mutation, *MYC* amplification status by performing targeted DNA sequencing at the laboratory of Pathology, CCR, NIH (if not included in the Natural History Study [CC 16C0151]).

5.1.1.1 Tissue blocks can be shipped to Department of Pathology at NCI at the following address:

Laboratory of Pathology
Center for Cancer Research
National Cancer Institute
[name]
[name]
Ph: [contact]

5.1.1.2 Procedures for storage of tissue specimens in the Laboratory of Pathology

Tissues designated for clinical diagnostics are transported to the Laboratory of Pathology (LP) where they are examined grossly, and relevant portions are fixed, embedded in paraffin and sectioned and stained for diagnostic interpretation. Unutilized excess tissues are stored for up to three months, in accordance with College of American Pathologists/Joint Commission on Accreditation of Healthcare Organizations (CAP/JCAHO) guidelines, and then discarded. Following completion of the diagnostic workup, the slides and tissue blocks are stored indefinitely in the LP's clinical archives. All specimens are catalogued and retrieved utilizing the clinical laboratory information systems, in accordance with CAP/JCAHO regulations. The use of any stored specimens for research purposes is only allowed when the appropriate IRB approval has been obtained. In some cases, this approval has been obtained via the original protocol on which the patient was enrolled.

5.1.2 Fresh frozen brain tumor tissue will be obtained if patient undergoes surgery at the time of disease progression. Pro-survival proteins, including Mcl-1, XIAP and survivin will be tested at protein by Western blot and at mRNA level by PCR in the NOB laboratory.

5.1.2.1 The samples should be shipped to the following address ON DRY ICE in appropriately labeled package in accordance with local and federal regulations for biological material:

[name] [name].
Neuro-Oncology Branch, NCI, NIH
[name]
[name]
Office: [contact] or [contact]
[contact]
[contact]

5.1.2.2 If the surgery is performed at Neurosurgery Department at NINDS, NIH, the following personnel will be contacted for tissue pick up.

[name] [name].
Neuro-Oncology Branch, NCI, NIH
[name]
[name]
Office: [contact] or [contact]
[contact]
[contact]

5.1.3 Pharmacokinetic (PK) and Pharmacogenetic (PG) Studies

5.1.3.1 Pharmacokinetic Studies

PK studies will be done in all patients that are enrolled in the cohort expansion part and the Post-Interim Analysis cohort. Blood samples for the determination of plasma levels of Zotiraciclib (TG02) will be obtained from each patient (see section [5.1.3.3](#) for schedule and tube types). Bioanalytical measurements for Zotiraciclib (TG02) will be conducted on an ultra HPLC-MSMS system using an assay developed and validated by the Clinical Pharmacology Program. This data will be used to monitor plasma concentrations of Zotiraciclib (TG02) to correlate to pharmacodynamic endpoints, clinical response, toxicity, and pharmacogenetic analyses.

5.1.3.2 Pharmacogenetic studies (PG)

PG studies will be done in all patients that are enrolled in the cohort expansion part and the Post-Interim Analysis cohort. One blood sample per patient (6mL) will be collected (see section [5.1.3.3](#) for schedule) to analyze the genomic DNA and assess genotype of the most relevant drug metabolizing enzymes and transporters (DMET). DNA will be analyzed on a DMET Plus (Affymatrix) genotyping platform that has the capacity to test for 1,936 genetic variations in 225 drug disposition genes, including 47 CYP (phase I metabolism) genes, 13 non-CYP (phase I metabolism) genes, 78 phase II metabolizing genes (including UGTs), 63 transporters, 4 genes involved in facilitation of drug transporters, 9 genes involved in global regulation of drug metabolizing/transporting proteins, 4 drug binding proteins.

Of specific interest to Zotiraciclib (TG02) are polymorphisms in CYP3A4, CYP1A2, and ABCB1 (P-glycoprotein), all of which are included in the DMET analysis.

The samples will be placed at room temperature. The date and exact time of each blood draw should be recorded on the sample tube and the PK/PG sheet. Contact [name] Pharmacology Program (Blood Processing Core) in [name] at [contact] at least 24 hours before transporting samples (the Friday before is preferred).

5.1.3.3 Sample Collection

PKs: Blood samples for the determination of plasma levels of Zotiraciclib (TG02) will be obtained from each patient via 6mL green sodium heparin tube collected on the first daily dose on cycle 1 day -3 at the following time points: pre-dose, 1hr, 2hr (peak), 4hr, 12hr, 24hr, 48hr, and 72hr post oral dose. For patients in the post-interim analysis cohort, blood will be collected, pre-dose, 1hr, 2hr, 4hr, 24hr, and 48hr post oral dose.

PGs: 6 mL of blood will be collected in an EDTA (purple top) tube on day -3 of cycle 1.

5.1.3.4 Sample processing

The samples will be placed immediately on wet ice and refrigerated. The date and exact time of each blood draw should be recorded on the sample tube and the PK sheet.

Please e-mail [contact] at least 24 hours before transporting samples (the Friday before is preferred).

For sample pickup, page [name].

For immediate help, call [contact] (main blood processing core number) or, if no answer, [contact] (main clinical pharmacology lab number).

For questions regarding sample processing, contact [contact].

Upon arrival in the Clinical Pharmacology Program, samples will be centrifuged, and the plasma transferred into cryovials for storage at -80 C until the time of analysis. In addition, samples will be barcoded.

5.1.4 Neutrophil analysis

Neutrophil analysis studies will be done in all patients that are enrolled in the cohort expansion part.

Three tubes of blood will be collected at all PK time points for the following studies: WBC and differential analysis, neutrophil morphology studies (photographs), neutrophil function assays, surface marker analysis and for spinning out cells and saving plasma to send to [name] for monitoring activation markers released into the plasma such as specific granule marker. (See section **5.1.4.1** for tube types and collection information. Note: The pediatric size tubes can be used as alternatives for blood sample collection, if it is necessary.)

WBC with differential and imaging analysis will be done at Department of Laboratory Medicine. Plasma and neutrophil isolation will be done by NOB laboratory and analysis will be done in Neutrophil Monitoring Laboratory (NML).

5.1.4.1 Collection

- a. CBC with differential (a tube of 6 cc blood collected in purple top tube) will be done on cycle 1 day -3 at the following time points*: pre-dose, 1hr, 2hr, 4hr, 12hr, 24hr, 48hr, and 72hr post oral Zotiraciclib (TG02). Neutrophil morphology will be studied by using Cellavision program.
- b. Collect blood sample (6 cc of blood in heparinized green top tube) at the time of PK sample collection for plasma isolation for monitoring neutrophil activation markers.
- c. Collect (6 cc of blood in purple top tube with EDTA), fix and stain neutrophils at the same time points of the PK sample collection. Samples will be used for neutrophil cell surface markers including but not limited to CD11a, CD11b, CD11c, CD32, CD18, CD67, CD64, CD18, CD45, CD62L, CD63, 7D5.

* All effort will be made to collect samples at prescribed time points; missed timepoints or collections outside the window (+/- 30 minutes from the scheduled time) will be documented but not constitute a deviation.

5.1.5 Labeling of Samples

Labels on all samples will at least include the following information:

- Patient initials, ID number
- Protocol number
- Collection date

5.2 SAMPLE STORAGE, TRACKING AND DISPOSITION

Samples will be ordered in CRIS and tracked through a Clinical Trial Data Management system. Should a CRIS screen not be available, the CRIS downtime procedures will be followed.

Samples will not be sent outside NIH without appropriate approvals and/or agreements, if required.

5.2.1 Clinical Pharmacology Program

All samples sent to the Clinical Pharmacology Program (CPP) will be barcoded, with data entered and stored in Labmatrix utilized by the CPP. This is a secure program, with access to Labmatrix limited to defined [name] lab personnel, who are issued individual user accounts. Installation of Labmatrix is limited to computers specified by [name]. These computers all have a password restricted login screen.

Labmatrix creates a unique barcode ID for every sample and sample box, which cannot be traced back to patients without Labmatrix access. The data recorded for each sample includes the patient ID, name, trial name/protocol number, time drawn, cycle time point, dose, material type, as well as box and freezer location. Patient demographics associated with the clinical center patient number are provided in the system. For each sample, there are notes associated with the processing method (delay in sample processing, storage conditions on the ward, etc.). Barcoded samples are stored in barcoded boxes in a locked freezer at either -20 or -80°C according to stability requirements. These freezers are located onsite in the CPP and offsite at NCI Frederick Central Repository Services in Frederick, MD. Visitors to the laboratory are required to be accompanied by laboratory staff at all times.

Access to stored clinical samples is restricted. Samples will be stored until requested by a researcher named on the protocol. All requests are monitored and tracked in Labmatrix. All researchers are required to sign a form stating that the samples are only to be used for research purposes associated with this trial (as per the IRB approved protocol) and that any unused samples must be returned to the CPP. It is the responsibility of the NCI Principal Investigator to ensure that the samples requested are being used in a manner consistent with IRB approval.

Following completion of this study, samples will remain in storage as detailed above. Access to these samples will only be granted following OHSRP/IRB approval of an additional protocol, granting the rights to use the material or if the use is not considered to be human subjects research.

5.2.2 Neutrophil Monitoring Laboratory (NML) / Frederick Laboratory

Plasma and neutrophil isolation will be done by NOB laboratory and analysis will be done in Neutrophil Monitoring Laboratory (NML) in Frederick.

Samples will be sent to the NOB laboratory and sent to Frederick laboratory will be barcoded with data entered and stored in the Labmatrix system utilized by the CCR, NCI. This is a secure system with access limited to defined personnel. All such personnel with access to patient information annually complete the NIH online Protection of Human Subjects course.

Labmatrix creates a unique barcode ID for every sample which cannot be traced back to patients without Labmatrix access. The data recorded for each sample includes the patient ID, name, trial name/protocol number, date/time drawn, as well as box and freezer location. Patient demographics associated with the Clinical Center patient number are provided in the system. For

each sample, there are notes associated with the processing method (delay in sample processing, storage conditions on the ward, etc.).

5.2.3 Department of Laboratory Medicine

Samples will be processed by the NOB laboratory and then sent to Department of Laboratory Medicine will be barcoded with data entered and stored in the Labmatrix system utilized by the CCR, NCI. This is a secure system with access limited to defined personnel. All such personnel with access to patient information annually complete the NIH online Protection of Human Subjects course.

5.2.4 Protocol Completion/Sample Destruction

All specimens obtained in the protocol are used as defined in the protocol. Any specimens that are remaining at the completion of the protocol will be stored in the conditions described below. The study will remain open so long as sample or data analysis continues. Samples from consenting subjects will be stored until they are no longer of scientific value or if a subject withdraws consent for their continued use, at which time they will be destroyed.

If the patient withdraws consent the participant's data will be excluded from future distributions, but data that have already been distributed for approved research use will not be able to be retrieved.

The PI will record any loss or unanticipated destruction of samples as a deviation. Reporting will be per the requirements of section 7.2.

6 DATA COLLECTION AND EVALUATION

6.1 DATA COLLECTION

The PI will be responsible for overseeing entry of data into an in-house password protected electronic system (C3D) and ensuring data accuracy, consistency and timeliness. The MDASI-BT responses will be entered by study subjects directly into Scribe/Labmatrix.

The principal investigator, associate investigators/research nurses and/or a contracted data manager will assist with the data management efforts. All data obtained during the conduct of the protocol will be kept in secure network drives or in approved alternative sites that comply with NIH security standards. Primary and final analyzed data will have identifiers so that research data can be attributed to an individual human subject participant.

All adverse events, including clinically significant abnormal findings on laboratory evaluations, regardless of severity, will be followed until return to baseline or stabilization of event.

Document AEs from the first study intervention, Study Day 1, through 30 days after the last administration of investigational agent/intervention. Adverse events that are serious need to be recorded through 30 days after the last administration of investigational agent/intervention. Beyond 30 days after the last intervention, only adverse events which are serious and related to the study intervention need to be recorded.

An abnormal laboratory value will be considered an AE if the laboratory abnormality is characterized by any of the following:

- Results in discontinuation from the study
- Is associated with clinical signs or symptoms
- Requires treatment or any other therapeutic intervention
- Is associated with death or another serious adverse event, including hospitalization.
- Is judged by the Investigator to be of significant clinical impact
- If any abnormal laboratory result is considered clinically significant, the investigator will provide details about the action taken with respect to the test drug and about the patient's outcome.

End of study procedures: Data will be stored according to HHS, FDA regulations and NIH Intramural Records Retention Schedule as applicable.

Loss or destruction of data: Should we become aware that a major breach in our plan to protect subject confidentiality and trial data has occurred, this will be reported expeditiously per requirements in section [7.2.1](#).

6.1.1 Non-Relevant Toxicities for Brain Tumor Protocols

Lymphopenia is a common finding among patients with primary brain tumors and is directly attributable to concurrent use of corticosteroids. To date, even Grade III lymphopenia has not been associated with a worsening of clinical outcome. Therefore, we will not consider this parameter in the determination of optimal dosing of drugs.

Weight gain is a common finding among patients with primary brain tumors. This too is directly attributed to the concurrent use of corticosteroids. Doses of steroids or study agents will not be modified as a consequence of weight gain. Corticosteroid dosage will be based on maintenance of control of edema in the brain and the standard clinical practice to use the minimal effective dose of corticosteroids will be employed.

Alopecia is a common occurrence in patients with brain tumors as a consequence of cranial radiotherapy. Alopecia will not be recorded or graded as toxicity.

Venous thromboembolic disease is a common complication occurring in up to 30% of patients with malignant gliomas.[\[47, 48\]](#) In this study, patients who develop deep vein thrombosis may receive anticoagulation and resume therapy once they are stable on anticoagulation. Grade III deep vein thrombosis will not be considered a DLT for the phase I portion.

The routine use of filgrastim or other white cell growth factors is not permitted during cycle 1 of the Phase I portion unless clinically indicated, but it may be used beyond this period or once the assessment of DLT has been completed.

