3.1.3 Definition of dose limiting toxicities (DLT)

All patients in the MTD finding phase of the phase I part will be evaluable for assessment of toxicity to define DLTs. The DLT-defining period is the first 4 weeks' treatment in the Phase I study.

Toxicities will be graded per the Common Terminology Criteria for Adverse events (CTCAE) Version 4.0. If multiple toxicities are seen, the presence of DLT should be based on the most severe toxicity experienced. DLT is defined as any of the following events occurring in the first cycle of treatment (4 weeks) and attributable to the study drugs:

- Any of the following hematological toxicities:
 - Grade 4 neutropenia lasting 5 days or more.
 - Febrile neutropenia defined as grade 3-4 neutropenia with fever $\geq 38.5^{\circ}\text{C}$ and/or infection requiring antibiotic or antifungal treatment.
 - Grade 4 thrombocytopenia lasting more than 2 days.
 - Grade 3 thrombocytopenia with bleeding of any duration

- Grade 3 or 4 anemia lasting more than 2 days.
- Any non-hematologic grade 3 or 4 toxicity, except the following
 - nausea or vomiting that responds to symptomatic therapy and lasts ≤ 7 days.
 - Diarrhea that responds to symptomatic therapy within 2 days.
 - fatigue that responds to symptomatic therapy and lasts ≤ 7 days.
 - weight gain (in patients on steroids)
 - venous thromboembolic disease (rationale for not including this event as a DLT described below)
- If there is a dose reduction of either or both study medications or if a dose is held or discontinued in cycle 1, this constitutes a DLT, per PI discretion.
- Grade 4 lymphopenia is not considered as a DLT for this study. All patients for this study have treated with alkylating agents and radiation treatment. Lymphopenia can be highly associated with the previous treatment or have a low threshold to have severe lymphopenia because of the previous treatments. In case of isolated laboratory abnormalities that may not reach clinical significance, a determination will be made by PI or in consultation with the IRB on a case-by-case basis to determine if DLT needs to be declared.
- Failure to recover from treatment related toxicities to be eligible for re-treatment within 4 weeks of the last dose of the drugs.

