3.3.1.1 Delay

For treatment on day 1 of each cycle (within the prior 72 hours), ANC $\geq 1.5 \times 10^9/L$, platelet count $\geq 100 \times 10^9/L$ and all grade 2 -3 non-hematologic AEs (except nausea and vomiting) must have resolved (to grade ≤ 1). For grade 4, discontinue treatment. For the purposes of this study, any clinically insignificant Grade 2 or 3 electrolyte abnormalities with attribution of unlikely related to or unrelated to study medications, will not require holding or dose-reducing study medications.

If AEs persist, treatment may be delayed by 1 week for up to 4 consecutive weeks. If, after 4 weeks of delay, all AEs have still not resolved to grade 1 or less: then any further treatment with temozolomide should be stopped, as summarized in Table 8 and Table 11.

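### The DLT exception for venous thromboembolism in 3.1.3 has no grade limit, while the rationale in 6.1.1 exempts only grade III; a drug-attributed grade 4 embolism is likely, but not certain, to be counted

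*Combined protocol and SAP*

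**What the plan says.** Section 3.1.3 sets the window and attribution requirement: "DLT is defined as any of the following events occurring in the first cycle of treatment (4 weeks) and attributable to the study drugs". Its non-hematologic clause reads "Any non-hematologic grade 3 or 4 toxicity, except the following", and one listed exception is "venous thromboembolic disease (rationale for not including this event as a DLT described below". That exception names no grade and no section. Section 6.1.1 is the only later text that supplies such a rationale. It notes that venous thromboembolic disease occurs in up to 30% of patients with malignant glioma, says that patients with deep vein thrombosis "may receive anticoagulation and resume therapy once they are stable on anticoagulation", and ends: "Grade III deep vein thrombosis will not be considered a DLT for the phase I portion".

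Two other bullets in 3.1.3 could still capture an excepted event. One covers dose reductions and held doses: "if a dose is held or discontinued in cycle 1, this constitutes a DLT, per PI discretion". The other is "Failure to recover from treatment related toxicities to be eligible for re-treatment within 4 weeks of the last dose of the drugs".

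On treatment after an event, 3.3.1.1 says "For grade 4, discontinue treatment", and Tables 8 and 11 do the same for non-hematologic grade 4. The footnote to Table 11 allows restart after a 2-week rest for grade 2 or 3 thrombosis. It describes grade 3 as uncomplicated pulmonary embolism and grade 4 as life-threatening pulmonary embolism.

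DLT counts feed the elimination row of Table 13, which also monitors cohort expansion (10.1), and the per-arm toxicity stop in Phase II (10.2). Section 10.2 does not define DLT.

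**The concern.** The exception is wider than the reason given for it. The reason is that thromboembolism is common in this disease and manageable, so that treatment can continue. It fits grade 3, but the protocol's own rules stop treatment at grade 4. The breadth also looks unintended. The neighbouring exceptions for nausea and vomiting, diarrhea, fatigue and weight gain each carry a limiting condition, and where 3.1.3 means to exempt a grade 4 toxicity (lymphopenia) it says so and explains why.

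At stake is whether a life-threatening embolism attributed to study drug enters the DLT count by rule or by judgement. The rule is still in use. Twelve patients are being added at 200 mg partly to characterize the dose-toxicity relationship, and Phase II has a DLT-based stop.

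**Working it through.** **Texts side by side, for a drug-attributed cycle-1 event**

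| Event | 3.1.3 exception | 6.1.1 | Treatment rule |
|---|---|---|---|
| Grade 3 | exempt | exempt | may restart after rest |
| Grade 4 | exempt (no grade limit) | not exempted | stop |
| Fatal | not named in the grade 3 or 4 clause | not exempted | – |

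The texts part at grade 4. Mandatory discontinuation makes the held-or-discontinued-dose bullet likely to apply, but that bullet is discretionary. The failure-to-recover bullet has no discretion clause. Its clock runs 4 weeks from the last dose, however, while the definition is confined to the first 4-week cycle, so its reach is arguable.

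**Table 13 reproduced.** Target φ = 0.35 (10.1). The protocol does not state the other BOIN settings, so the usual defaults are assumed: φ1 = 0.6φ = 0.21 and φ2 = 1.4φ = 0.49, with elimination when Pr(p > 0.35 | data) > 0.95 under a Beta(1,1) prior.

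- λe = ln[(1−φ1)/(1−φ)] / ln[φ(1−φ1)/(φ1(1−φ))] = ln(0.79/0.65) / ln(0.2765/0.1365) = 0.276
- λd = ln[(1−φ)/(1−φ2)] / ln[φ2(1−φ)/(φ(1−φ2))] = ln(0.65/0.51) / ln(0.3185/0.1785) = 0.419

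For n = 3, 6, 9, 12, 15, 18 this gives escalate ≤ 0/1/2/3/4/4, de-escalate ≥ 2/3/4/6/7/8 and eliminate ≥ 3/5/6/7/9/10. All 18 printed entries match. One event can change a decision: 0/3 escalates, 1/3 stays, 2/3 de-escalates. Escalation is complete, though, so what remains live is the elimination row.

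**Table 16 reproduced.** An exact binomial recursion over the printed boundaries 4/5, 6/10, 10/20, 15/30 gives the following.

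| True rate | 0.2 | 0.3 | 0.4 | 0.5 | 0.6 |
|---|---|---|---|---|---|
| Recomputed | 0.013 | 0.093 | 0.344 | 0.712 | 0.943 |
| Printed | 0.014 | 0.096 | 0.345 | 0.716 | 0.939 |

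The largest difference is 0.004.

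**Effect of counting the events.** The documents give no rate v for drug-attributed, cycle-1, grade 4 thromboembolism. The 30% in 6.1.1 is overall occurrence in the disease. I assume v = 0.5%, 1% and 2%, and base DLT rates b of 20% and 30%. Combined rate = 1 − (1−b)(1−v); for example, b = 0.30 and v = 0.02 give 1 − 0.70 × 0.98 = 0.314.

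| Stopping rule | b | v = 0 | 0.5% | 1% | 2% |
|---|---|---|---|---|---|
| Phase II, per arm | 20% | 0.013 | 0.014 | 0.015 | 0.018 |
| Phase II, per arm | 30% | 0.093 | 0.098 | 0.104 | 0.116 |
| Elimination row, 12 patients | 20% | 0.013 | 0.014 | 0.015 | 0.017 |
| Elimination row, 12 patients | 30% | 0.065 | 0.068 | 0.072 | 0.079 |

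The largest change is 0.116 − 0.093 = 0.023. The 12-patient rows use boundaries 3/3, 5/6, 6/9 and 7/12. They are illustrative, because they ignore patients already treated at 200 mg, whose number is not given.

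**Chance that the question arises at all**, 1 − (1−v)^n: at v = 1%, 11% for n = 12 and 33% for n = 40; at v = 2%, 22% and 55%.

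**The case against.** The strongest reply is that grade 4 is largely handled already. Discontinuation is mandatory, a discontinued cycle-1 dose is a DLT unless the PI decides otherwise, and a permanently stopped patient never becomes eligible for re-treatment. Reading the cycle-1 window so as to defeat the failure-to-recover bullet would leave that bullet little effect. This stands in large part and is why the gap is small: what is left is discretion where a fixed rule would be expected.

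The rationale in 6.1.1 also opens with a disease-level reason that carries no grade. That is true, but its operative sentence is limited to grade III.

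It is fair, too, that the probabilities above are upper bounds. They treat every such event as uncounted now, meaning that the PI always declines and failure to recover never applies.

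Three stronger readings are tempting and are not supported:

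- **That life-threatening embolisms go uncounted.** Both indirect routes exist, and nothing in the documents shows that such an event has occurred.
- **That the Phase II stop is blind to thromboembolism.** Section 6.1.1 confines its exemption to Phase I, 3.1.3 sets its DLT period for the Phase I study, and 10.2 does not import the exemption.
- **That the 2-week rest routinely turns an exempt grade 2 or 3 event into a DLT.** A 14-day rest starting at onset removes a cycle-1 dose for 26 of 28 onset days (dose-dense) or all 28 (metronomic). A missed dose is still a DLT only at PI discretion, and the specific exception gives the PI a reason not to call it.

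The absence of a fatal grade from the clause applies to every toxicity and is not particular to this one.

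**Conclusion.** The mismatch between 3.1.3 and 6.1.1 is real and worth correcting, at the level of a point to consider. As written, a drug-attributed cycle-1 grade 4 embolism is excluded by the exception and is likely, but not certain, to be counted by another route. The change in stopping probability is at most about 0.02, given the assumed 0.5% to 2% event rates and base DLT rates of 20% and 30%, and assuming that every such event is now missed. The Phase II figures further assume that the exemption would carry into Phase II, which the documents do not say. The consequence is limited further because the MTD has been identified, the added cohort receives a lower dose, the RP2D depends on the PFS4 difference, and attribution stays a judgement under any wording. No printed boundary or table value is wrong.

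**What to change.** 1. In 3.1.3, change the exception to: *grade 3 venous thromboembolic disease (see 6.1.1)*.
2. In 3.1.3, add a separate bullet outside the exception list, so that an inclusion does not sit under an exclusion heading: *Grade 4 or fatal venous thromboembolism attributable to study drug is a DLT.*
3. Align 6.1.1 to the same grade limit and keep its restriction to Phase I.
4. Do not extend the grade 3 exemption to the Phase II toxicity stop in 10.2; that would loosen a safety rule.
5. Check the safety records for any earlier grade 4 or fatal thromboembolic event left uncounted. Re-score it, or report DLT counts under both definitions.

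The cost is a few sentences and a records check, with no new data and no change to boundaries or sample size. The downside is a slightly different DLT definition for earlier and later patients, which matters in a cohort meant to characterize dose and toxicity. Step 5 handles it.
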